19. FIGURES

Figure 1: NEAT Study Flow-Chart for Year # 1 (2020)

[figure not shown]

Figure 2: NEAT Study Flow-Chart for Year # 2 (2021)

[figure not shown]

Figure 3: Individual Visit Flow-Chart – Screening (Visit # 1)

[figure not shown]

Figure 4: Individual Visit Flow-Chart – Baseline Assessment (Visit # 2)

[figure not shown]

Figure 5: Individual Visit Flow-Chart – Follow-Up # 1 (Visit # 3)

[figure not shown]
[figure not shown]

Figure 6: Individual Visit Flow-Chart – Follow-Up # 1 (Visit # 4)

[figure not shown]
[figure not shown]

Figure 7: Individual Visit Flow-Chart – 4-12 Month Safety Check (Visit # 5)

20. APPENDIX A – SAMPLE PROCUREMENT AND PROCESSING

Blood Sample Collection

Every effort must be made to make venipuncture as easy and painless as possible for participants. The technician must remain calm and project an attitude of competence even when faced with the most nervous or inquiring participant. The best way to achieve this is for the technician to be thoroughly knowledgeable about all aspects of the procedures. This study involves the collection of a total of ~45 ml of blood. Any participant who is concerned about the volume of blood should be reassured that the total amount of blood drawn is about 1.5 ounces, although it may look like more.

Blood Collection Tray and Tubes Preparation

Prior to venipuncture the tray is prepared for each participant. Each tray holds the Vacutainer tubes used in blood collection labeled with the subject identifier code (given by the research coordinator), date, type of blood being collected (serum whole blood, EDTA plasma, sodium citrate plasma, etc.) and the study visit (Visit # 1, 2, 3, 4).

Blood Collection Procedure

General Guidelines

Venipuncture should be performed using standard sterile technique in the sitting position. Handle all specimens as potentially infectious for laboratory workers. OSHA rules mandate that technicians must always wear disposable protective gloves when collecting and processing specimens. All needles and sharps must be discarded into puncture resistant containers. Avoid formation of potentially infectious aerosols when removing the rubber stoppers from Vacutainer tubes. In addition to wearing protective gloves, hold a piece of gauze over the stopper while slowly removing it from the tube. Place all used Vacutainer tubes and blood-contaminated products in biohazard bags for proper disposal. Use 0.5% sodium hypochlorite (household bleach diluted 1: 10) to clean up any spills of blood, plasma, or serum.

For Extremely Apprehensive Participants: Do not under any circumstances force the participant to have blood drawn. It may help to explain to the subject that the blood drawing is designed to be nearly painless as possible. It may also be helpful to have the participant relax in the blood drawing chair just so the phlebotomist can check the veins in the participant's arms, without actually drawing blood. If the participant is very anxious, he/she may lie down during the blood draw. Give the participant enough time to feel comfortable after the blood collection, as well. In many cases the most memorable part of the experience for participants will be the contact with the technicians who draw the blood and their general attitude and competence.

Procedure

Before applying the tourniquet, screw the Luer adapter into the plastic Vacutainer tube guide. Insert the butterfly tubing onto the adapter. With jacket or sweater removed, have the participant sit upright with the sleeves rolled up to expose the antecubital fossa.

Wrap the tourniquet around the arm 3 to 4 inches (7.5 to 10.0 cm) above the venipuncture site. If the participant has a skin problem, put the tourniquet over the participant's shirt or use a piece of gauze or paper tissue so as not to pinch the skin. The tourniquet should be on the arm for the shortest time possible. Never leave the tourniquet on for longer than two (2) minutes. To do so may result in hemo-concentration or a variation in blood test values. If a tourniquet must be applied for preliminary vein selection, and it remains on the arm for longer than two minutes, it should be released and reapplied after a wait of two minutes.

Venipuncture:

1. Identify the vein, and then cleanse the venipuncture site.
2. Remove the alcohol prep from its sterile package.
3. Cleanse the vein site with the alcohol prep using a circular motion from the center to the periphery.
4. Allow the area to dry to prevent possible hemolysis of the specimen and a burning sensation to the subject when the venipuncture is performed.
5. If venipuncture becomes difficult, the vein may need to be touched again with your hand. If this happens, cleanse the site again with alcohol.

After successful venipuncture:

1. Place tubes into the Vacutainer holder.
2. Grasp the participant's arm firmly, using your thumb to draw the skin taut. This anchors the vein. The thumb should be 1 or 2 inches below the venipuncture site.
3. With the needle bevel upward, enter the vein in a smooth continuous motion.
4. Make sure the participant's arm is in a flat or downward position while maintaining the tube below the site when the needle is in the vein. It may be helpful to have the participant make a fist with the opposite hand and place it under the elbow for support.
5. Grasp the flange of the needle holder and push the tube forward until the butt end of the needle punctures the stopper, exposing the full lumen of the needle. The tube should begin filling with blood.
6. Remove the tourniquet after tube #1 fills.
7. Keep a constant, slight forward pressure (in the direction of the adapter) on the end of the tube. This prevents release of the shutoff valve and stopping of blood flow.
8. Fill each Vacutainer tube as completely as possible; i.e. until the vacuum is exhausted and blood flow ceases. If a Vacutainer tube fills only partially, remove the tube and attach another without removing the needle from the vein.
9. When the blood flow into the collection tube ceases, remove the tube from the holder. The shutoff valve covers the point, stopping blood flow until the next tube is inserted (if necessary).

The tubes should be gently inverted 6-8 times immediately following removal of the tube from the adapter.

If a blood sample is not forthcoming, the following **manipulations** may be helpful.

1. Turn needle slightly or lift the holder in an effort to move the bevel away from the wall of the vein.
2. Move needle slightly in hope of entering vein. Do not probe. If not successful, release tourniquet and remove needle. A second attempt can be made on either arm.
3. Loosen the tourniquet. It may have been applied too tightly, thereby stopping the blood flow. Reapply the tourniquet loosely. If the tourniquet is a Velcro type, quickly release and press back together. Be sure, however, that the tourniquet remains on for no longer than two minutes at a time.

At the conclusion of the draw

1. To remove the needle, lightly place clean gauze over venipuncture site.
2. Remove the needle quickly and immediately apply pressure to the site with a gauze pad.
3. Discard needle and its cap into needle box (DO NOT ATTEMPT TO RECAP NEEDLES!)
4. Have the participant hold the gauze pad firmly for one to two minutes to prevent a hematoma.

Bandaging the arm under normal conditions:

1. Slip the gauze pad down over the site
2. Continue mild pressure.
3. Apply an adhesive or gauze bandage over the venipuncture site
4. Make sure that blood flow has stopped.

Bandaging the arm if the participant continues to bleed:

1. Apply pressure to the site with a gauze pad.
2. Keep the arm elevated until the bleeding stops.
3. Wrap a gauze bandage tightly around the arm over the pad.
4. Tell the participant to leave the bandage on for at least 15 minutes.

Blood Collection Precautions when a subject feels faint or looks faint following the blood draw:

1. Have the person remain in the chair. If necessary, have him/her lie on the floor with their legs elevated. Use of a transfer belt may be indicated in this situation.
2. Take an ampule of smelling salts, crush it, and wave it under the person's nose for a few seconds.
3. Provide the person with a basin if he/she feels nauseous.
4. Have the person stay seated or lying down until the color returns and he/she feels better.
5. Have someone stay with the person to prevent them from falling and falling and injuring themselves if they should faint.

6. Place a cold wet cloth on the back of the person's neck or on their forehead.
7. Once the episode has passed, some fruit juice may be given to the participant in order to counteract any possible hypoglycemia due to fasting.
8. If the person continues to feel sick, take a blood pressure and pulse reading. Contact a medical staff member, who will advise you on further action.

Blood Tube Labeling and Processing

[figure not shown]
For the study, a total of approximately 45mL blood will be drawn into different tubes with or without internal coating of anticoagulants. Biomedical analysis of genetics will be performed only if the subject has consented to the genetic sub-study. It is important that the technician know more than just the arrangement of the blood collection tubes and the sequence of the tube collection. He/she should also be familiar with the purpose of each tube, the type of anticoagulant in-each tube, and possible sources of error in the handling of each tube.

Each tube should be labeled with the subject's ID code (given by the study coordinator), study ID, the date, tube type, and time point (visit # 1, 2, 3, 4)

After blood draw, all labeled tubes should be kept in a cooler until further processing and storage.

Urine Collection

Standard clean catch urine sample will be obtained in sterile cups from participants. The samples will be transported on ice to the Diabetes and Obesity Center's research laboratory on the 4th floor of the Delia Baxter building for storage and mass spectrometric analysis. Urine samples not being processed immediately maybe placed in a biospecimens only refrigerator.

21. APPENDIX B – MEASUREMENT OF BLOOD BIOMARKERS

[figure not shown]
Endothelial Progenitor Cells (EPCs)

Eight ml of venous blood collected in a CPT Mononuclear Cell preparation tube (Becton Dickinson) will be processed within 3 hours of collection. Mononuclear cells will be separated by centrifugation at 1700g for 30 minutes. The buffy coat layer will be collected and washed twice with PBS+1%BSA. Cells will be pelleted by centrifugation at 400g for 5min and incubated with Fc Block for 10 minutes (Miltenyi Biotec). 50ul aliquots will be then incubated with FITC anti-CD41a (BD Biosciences), FITC-CD235a (eBioscience), FITC-CD16 (eBioscience), QDot655anti-CD14 (Invitrogen), PE-CF594 anti-CD34 (BD Biosciences), APC anti- AC133 (Miltenyi Biotec), V450 anti-CD31 (BD Biosciences), V500 anti-CD45 (BD Biosciences). In addition, we will include a discriminator of cell viability (Live Dead Green; Becton Dickinson). An unstained cell aliquot will be used as a control. After a 30 min incubation, the cells will be washed, resuspended in PBS+1%BSA, and 50ul of volumetric counting beads (Accucount Particles; Spherotech) added. The samples will be then run on an LSR II flow cytometer (Becton Dickinson) set to acquire 20,000 beads. Collected events will be analyzed using FlowJo software. Initial gating will be selected a lymphocyte population that was negative for CD235a, CD41a, CD16, CD14 and the viability marker. Fifteen distinct EPC subgroups will be then identified by the variable expression of CD31, CD45, CD34, and AC133 (S1 Table). Positive boundaries for gating will be accomplished with the unstained sample. EPCs numbers will be quantified and normalized to volume of blood using bead counts.

Microparticles and Platelet-Monocyte Aggregates (PMA)

For the analysis of microparticles and immune cell populations, 8 ml of blood will be collected in sodium citrate-containing cell preparation tubes (CPT Vacutainer; Becton Dickinson). These tubes will be centrifuged at 1700xg for 30 min at room temperature and shipped overnight to the University of Louisville for analysis. Upon arrival, the tubes will be centrifuged again and the upper layer containing mononuclear cells and plasma was collected. This material will be diluted with an equal volume of PBS and centrifuged at 500xg for 10 min. Aliquots of the supernatant will be used for analysis of microparticles while the cell pellet will be washed once with PBS and centrifuged. The final cell pellet will be resuspended in a volume of 300 μ l PBS+2% FCS, 150 μ l of which will be used for analysis of immune cell populations.

For analysis of platelet-monocyte aggregates, 3ml of blood will be collected in an acid-citrate dextrose tube (ACD Vacutainer; Becton-Dickinson), and then 1ml aliquots will be diluted with 3ml PBS and fixed with 1.3ml of 4% paraformaldehyde for 30 min on ice. Red blood cells will be lysed by addition of 24 ml of water, the samples will be centrifuged at 400xg for 10min and the cell pellet will be resuspended in 1 ml Tyrode's buffer and shipped to University of Louisville as above.

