Primary Endpoints (reflecting change from baseline to 6 weeks and 12 weeks and between groups)

1. Difference in EPC-2 between Carnosine and Placebo Groups
2. Difference in EPC-3 between Carnosine and Placebo Groups
3. Difference in EPC-4 between Carnosine and Placebo Groups
4. Difference in EPC-7 between Carnosine and Placebo Groups
5. Difference in EPC-8 between Carnosine and Placebo Groups

Secondary Endpoints (reflecting change from baseline to 6 weeks and 12 weeks and between groups)

1. Difference in Arterial Stiffness between Carnosine and Placebo Groups
2. Difference in Endothelial Microparticles between Carnosine and Placebo Groups
3. Difference in Platelet Monocyte Aggregates between Carnosine and Placebo Groups

Data Collection Tools

Blood Samples

A sample of ~3 table spoons (~45 ml) of blood will be obtained by venipuncture performed by a study staff trained in phlebotomy using standard procedures and precautions to insure the safety of the participants and phlebotomist. If any subject becomes ill, uncomfortable, or desires to withdraw, he/she may do so at any time. Blood sample collection protocol is detailed in Appendix A. Samples will be promptly transported to the Diabetes and Obesity Center's research laboratory on the 4th floor of the Delia Baxter building ([name]) for processing, storage, and analysis. After processing, samples will be aliquoted in appropriately labeled vials and stored in (-80C) freezer. Stored samples will contain study name, participant ID, date of sample acquisition, type of sample, and visit type. Samples will be stored in de-identified fashion and participant personal information or PHI will not be displayed/barcoded on any stored sample. Samples will be stored for future use, ancillary studies, and or preliminary data development.

The measurement of blood biomarkers for primary and secondary endpoints from blood samples (EPCs, microparticles, and PMA) are further detailed in Appendix B.

Urine Samples

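### Appendix B ships the unfixed microparticle tube overnight to Louisville, contradicting Section 8's prompt local transport; for platelet-monocyte aggregates the gap is a missing draw-to-fixation time

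*Combined protocol and SAP*

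**What the plan says.** Section 8 (Data Collection Tools, Blood Samples) gives a local route: "Samples will be promptly transported to the Diabetes and Obesity Center's research laboratory on the 4th floor of the Delia Baxter building". It then passes the detail on: "The measurement of blood biomarkers for primary and secondary endpoints from blood samples (EPCs, microparticles, and PMA) are further detailed in Appendix B".

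Appendix B gives the microparticle tube a different route: "These tubes will be centrifuged at 1700xg for 30 min at room temperature and shipped overnight to the University of Louisville for analysis". The next step is "Upon arrival, the tubes will be centrifuged again and the upper layer containing mononuclear cells and plasma was collected". For PMA, the blood is diluted and "fixed with 1.3ml of 4% paraformaldehyde for 30 min on ice"; red cells are lysed and the pellet resuspended, and only then is it "shipped to University of Louisville as above".

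The EPC paragraph of the same appendix has no shipping step and sets a 3-hour limit from collection to processing. Neither of the other two assays has a time limit.

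Appendix A (Blood Tube Labeling and Processing) adds a general rule that after the draw "all labeled tubes should be kept in a cooler until further processing and storage". It gives no temperature and no maximum time.

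**The concern.** Laboratory staff have two routes for the same blood draw, and the more detailed one is the overnight route. Under it, the microparticle tube travels with unfixed cells still in contact with the plasma that will be measured. Any particles released in the tube during the hold could not be told apart from those present in the participant at the draw. The length of the hold is not controlled beyond the word overnight.

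Endothelial microparticles are one of three listed secondary endpoints and the measure behind the research question on endothelial damage. PMA is another and serves the question on platelet activation. Its exposure is different and smaller: the documents do not say how long, or under what condition, the blood may wait before fixation.

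**Working it through.** The plan gives no figure on this point, so the check is a comparison of texts followed by a short argument about precision.

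1. **Where blood is drawn.** Section 9 requires participants to live within 30 miles of Louisville. Section 11 describes University of Louisville personnel as those with participant contact and those who process and analyse. It also stores the supplements, which Section 10 has handed out at Visits 2 and 3, at the university's Clinical Trials Unit. The only other institution with a role in conduct, the University of Colorado pharmacy, makes capsules. No remote site is described. No clinic address is given, so local drawing is a strong inference and not a stated fact.

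2. **Microparticles under Appendix B.** Draw; spin at room temperature; overnight shipment; second spin; collect a layer holding both mononuclear cells and plasma; dilute; spin at 500xg; read the supernatant. There is no fixation step, and cells are parted from the measured fluid only in the last spin, after transit.

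3. **PMA under Appendix B.** Draw; dilute; fix; lyse; spin; resuspend; ship. Only fixed cells travel. The uncontrolled interval runs from draw to fixation, during which Appendix A's cooler rule applies.

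4. **EPCs under Appendix B.** Processing within 3 hours, no shipment. This is also a CPT tube, from the same visit. The primary endpoints are therefore outside the conflict, and the laboratory must already be able to handle a CPT tube within that time.

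5. **Effect on the comparison.** Suppose handling adds an error with mean m and variance h² to a continuous outcome whose variance is s², with the same distribution in both blinded arms.
   - The expected difference is (carnosine mean + m) − (placebo mean + m) = carnosine mean − placebo mean. The error cancels.
   - With the planned 120 completers per arm, the standard error at one visit is √[(s² + h²)(1/120 + 1/120)] = √[(s² + h²)/60], against √(s²/60) without the error. Precision falls.
   - For change from baseline with independent errors at the two visits, the variance of the change rises by 2h².
   - If baseline and follow-up take different routes, the change also carries the difference between the two routes' means. That cancels between arms when the mix of routes is the same in both.

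   The documents give neither s nor h for microparticles or PMA, so the loss cannot be put into numbers.

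**The case against.** The strongest reply is that this is a drafting leftover and not a plan to age samples. Shipping to the trial's own institution makes little sense, one verb in the microparticle paragraph slips into the past tense, and Section 8 already gives the sensible route. That may well be so, although the documents do not say it. It makes the harm conditional; it does not remove the contradiction, because Section 8 itself sends the reader to Appendix B.

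Four stronger readings are tempting, and the documents do not support them:

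- **That both endpoints would be read on day-old blood.** PMA cells are fixed before they travel.
- **That the noise pulls a true difference toward zero.** Equal random error in a continuous outcome leaves the expected mean difference unchanged. It widens the interval and lowers power; only a standardised effect shrinks.
- **That the loss can be stated as a share of effect or sample size.** No SD, reliability or storage figure is given for either marker, and the endpoints are defined as changes from baseline, so an assumed single-visit variance would not describe them.
- **That the artefact varies with season.** All intervention visits fall between May and September, both arms share that calendar, and no courier times are given.

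A blanket exemption of CPT tubes from the cooler rule would also go too far. The EPC tube is a CPT tube, so the exemption would alter handling for all five primary endpoints.

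**Conclusion.** The contradiction stands. As written, Appendix B exposes the microparticle endpoint to an avoidable, uncontrolled overnight hold of unfixed material. For PMA a narrower gap remains: no draw-to-fixation limit, combined with a general cooler rule that states no temperature. The consequence is possible added variability and lower precision in both arms, of unknown size, with no bias between arms.

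This rests on three assumptions: that blood is drawn in the Louisville area, that Appendix B is followed at some or all visits, and that handling does not depend on the assigned arm. The primary EPC endpoints are unaffected. The point deserves correction before samples are collected, because late processing cannot be undone afterwards, but it does not threaten the trial's main conclusion.

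**What to change.** Reconcile Section 8, Appendix A and Appendix B so that one route remains:

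- Delete the overnight shipment from both the microparticle and PMA paragraphs of Appendix B, and process at the local laboratory on the day of the draw.
- State one maximum time from draw to separation of plasma from cells for microparticles. The 3-hour EPC limit is already workable for a CPT tube from the same visit.
- State one maximum time from draw to fixation for PMA.
- State the holding condition before processing for these two tubes, leaving handling of the EPC tube as it is.
- Log draw, separation and fixation times for each visit, so that handling can be checked.

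The cost is appendix wording, a time log and some same-day bench time. Sample size and the primary analysis do not change.

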23. APPENDIX D – SUPPLEMENT MANUFACTURING AND QUALITY CONTROL PROTOCOL

L-Carnosine Powder Certificate of Analysis

The certificate of analysis for the L-Carnosine powder from www.bulksupplements.com is attached. It highlights that the dietary supplement conforms the regulatory standards.

Supplement Compounding and Quality Control Standard Operating Protocol

The capsule sources, compounding methods, quality control measures and other standard operating protocol are detailed in the attached agreement letter from the University of Colorado Skaggs School of Pharmacy and Pharmaceutical Sciences.

24. APPENDIX E – PHYSICAL FUNCTION MEASUREMENTS

Handgrip Strength Test

[figure not shown]
The first is the handgrip strength test, which assesses upper extremity strength and is reported to be a reliable indicator of a variety of impaired cardiopulmonary conditions.^{49, 50} The handgrip strength static test will be assessed as described⁵¹ using a Jamar Technologies Plus+ Digital Hand Dynamometer (JLW Instruments, Chicago, IL, USA). Subjects will be seated in an upright position with their shoulder adducted and elbow flexed at 90°, with the forearm allowed to rest lightly on the arm of the chair or on the subject's thigh. For each subject, a maximal voluntary contraction will be determined as the highest of three initial contractions (INITIAL MAX).⁵² After a one-minute rest period subjects will be instructed to squeeze the dynamometer in a static contraction at a level of 50% of their maximal voluntary contraction for as long as possible, and the duration recorded (DURATION).⁵³ The level of static contraction will be monitored by the assessor who provides verbal feedback to ensure that a level of 50% maximal voluntary contraction is maintained. Subjects will then perform an additional post-fatigue maximal contraction within 10 seconds of completion of the 50% maximal static contraction (FINAL MAX). Handgrip testing will be performed on both the dominant and non-dominant hands for each subject. In addition to (INITIAL MAX), (FINAL MAX) and (DURATION), additional calculated indices will be: a) work performed (WORK = DURATION x 50% INITIAL MAX); and b) Strength Decrement Index (SDI = 100 x (INITIAL MAX + FINAL MAX)/INITIAL MAX).

Two Minute Step Test (2MST)

The 2MST is an assessment of aerobic endurance and can be predictive of morbidity and mobility in older adults or those with CVD. Higher scores on the 2MST indicate increased functionality, quality of life, and decreased incidence of chronic health problems.⁵⁴ To perform the test, participants are asked to stand next to a wall and march in place with the intent of raising the knees to a marked target on the wall mid-way, representing a height between the lateral condyle and anterior superior iliac spine of the participant. The test administrator counts the number of times the right knee reaches the marked target over a 2-minute period. If an individual cannot march for the full 2-minutes, they are permitted to take a standing or seated rest break and resume within the 2 minutes.⁵⁵

Bilateral Calf-Raise Test

This is a muscle strength and endurance test that has been used to evaluate the functional performance of older adults and those with CVD.⁵⁶⁻⁵⁹ Initially, participants will stand barefoot and in a bipedal position facing a wall and will be supported with their dominant hand on the wall and elbow in semi-flexion to maintain balance. The participant will perform plantar flexion with maximum range for all repetitions. The first flexion is executed using the full range of motion, up to the point of support on the metatarsophalangeal joints. At full flexion, the examiner marks the maximum height reached by the participant's head with an adjustable height instrument. This will ensure that the individual performs plantar flexion using full range of motion in every

repetition. A verbal command will be given to start the test and the participant will perform the maximum number of plantar flexions possible, as fast as possible until the point of voluntary fatigue. Measurements include the number of plantar flexions performed during the bilateral calf-raise, total time in seconds, and repetition rate (repetitions per second). These outcomes can then be normalized for differences in participant physical characteristics such as BMI, height, weight and age.

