6. STUDY OBJECTIVES

Primary Objective

The primary purpose of this study is to determine whether taking carnosine as a dietary supplement protects the vasculature from PM_{2.5} air pollution-induced oxidative stress in healthy human subjects. The primary endpoint is difference in EPCs between Carnosine versus placebo groups at 6 weeks and 12 weeks.

Secondary Objective

The secondary objective of this study is to determine whether taking carnosine as a dietary supplement is protective from PM_{2.5} air pollution-induced arterial dysfunction, endothelial damage, and pathological platelet activation in healthy human subjects. The secondary endpoints are difference in arterial stiffness, endothelial microparticles, and platelet monocyte aggregates between Carnosine versus placebo groups at 6 weeks and 12 weeks.

Hypothesis (for Primary and Secondary Objectives)

Carnosine supplementation blunts adverse effects of PM_{2.5} pollution on vasculature of healthy participants.

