SphygmoCor will be used to measure indices of arterial stiffness (augmentation index; AI, augmentation pressure; AP, pulse wave velocity; PWV, aortic systolic pressure, and SEVR).

SphygmoCor is a non-invasive, cuff-based tool used for obtaining brachial artery blood pressure and the central arterial pressure waveform with associated indices (augmentation index, augmentation pressure, and pulse wave velocity). A cuff will be applied on the upper arm in the standard position. The cuff will be partially inflated to record the brachial waveforms. These waveforms are detected by sensing changes in the pressure inside the cuff related to arterial pulsation. The ascending aortic waveform is subsequently derived using a validated mathematical transfer function.

Arterial stiffness test will be administered by a research team member at baseline assessment (Visit # 2) and then at each additional clinical study visit from baseline onwards (Visit # 2 through Visit # 4). Arterial stiffness testing (via SphygmoCor) is detailed in Section 8 “Investigational Plan”.

Physical Function Test

To assess the impact of carnosine supplementation on physical performance during times of variable PM_{2.5} levels, we will utilize three physical performance tests: handgrip strength test, 2-minute step test (2MST), and bilateral calf-raise test.

Physical function test will be administered by a research team member at baseline assessment (Visit # 2) and then at each additional clinical study visit from baseline onwards (Visit # 2 through Visit # 4). Testing protocol is detailed in Section 8 “Investigational Plan” and Appendix E.

Environmental Pollution Exposure Questionnaire

This questionnaire will assess participant’s exposure to environmental pollution. It will be administered by a research team member at baseline assessment (Visit # 2), Follow-Up # 1 (Visit # 3) and Follow-Up # 2 (Visit # 4).

Sleep Questionnaire

This questionnaire will assess participant’s sleep habits during the study period. It will be administered by a research team member at baseline assessment (Visit # 2), Follow-Up # 1 (Visit # 3) and Follow-Up # 2 (Visit # 4).

[figure not shown]
Diet and Exercise Questionnaire

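### Appendix E defines the Strength Decrement Index with a plus sign, so it falls as strength loss grows; a minor error, since the index is outside the listed endpoints and can be recomputed

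*Combined protocol and SAP*

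**What the plan says.** Section 24 (Appendix E), under Handgrip Strength Test, sets out the two measurements that enter the index. Pre-fatigue strength is the best of three attempts: "a maximal voluntary contraction will be determined as the highest of three initial contractions (INITIAL MAX"). Post-fatigue strength comes from one "additional post-fatigue maximal contraction within 10 seconds of completion of the 50% maximal static contraction (FINAL MAX"). The appendix then lists derived quantities, among them the Strength Decrement Index: "SDI = 100 x (INITIAL MAX + FINAL MAX)/INITIAL MAX".

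No other section restates the index, gives an expected range, or says which direction is favourable. Appendix E does give a direction for the 2-minute step test (higher is better), but none for this index.

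Section 12, Physical Function Test, gives the purpose of the tests: "To assess the impact of carnosine supplementation on physical performance during times of variable PM_{2.5} levels, we will utilize three physical performance tests". Handgrip is one of the three. They are given at baseline and repeated at Visits 3 and 4, so change by arm can be examined.

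The physical function tests are not among the endpoints. The primary endpoints are five EPC measures, and Section 6 names the others: "The secondary endpoints are difference in arterial stiffness, endothelial microparticles, and platelet monocyte aggregates between Carnosine versus placebo groups at 6 weeks and 12 weeks". Section 15 names no analysis of handgrip or of this index.

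**The concern.** A quantity called a decrement should be zero when nothing is lost and should grow with the loss. The printed formula adds post-fatigue strength to pre-fatigue strength, so it is largest when nothing is lost. The name and the formula point in opposite directions, and the plan offers nothing else to settle which one a programmer or reader should follow.

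What is at stake is the reading of one derived variable. If the formula is coded as printed and the result is read by its label, a supplement that preserves grip after fatigue would show a higher decrement and look unfavourable. Any summary given as a percent change or ratio of the index would also be wrong in size as well as direction.

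**Working it through.** **Inputs.** The formula and the definitions of INITIAL MAX and FINAL MAX come from Appendix E. The plan gives no numerical value for the index, so there is no figure of its own to reproduce. The grip values below are assumed, in arbitrary units, and serve only to show the behaviour of the formula.

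**Algebra.** Let r = FINAL MAX/INITIAL MAX, the fraction of strength retained.

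- As written: 100 × (INITIAL + FINAL)/INITIAL = 100(1 + r).
- With a minus sign: 100 × (INITIAL − FINAL)/INITIAL = 100(1 − r).
- Sum of the two: 100(1 + r) + 100(1 − r) = 200 for every r. The written index is therefore 200 minus the minus-sign index.

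**Values for INITIAL MAX = 40 (assumed).**

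| FINAL MAX | As written | With minus |
|---|---|---|
| 40 | 200 | 0 |
| 36 | 190 | 10 |
| 32 | 180 | 20 |
| 28 | 170 | 30 |
| 20 | 150 | 50 |
| 0 | 100 | 100 |

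The 100 to 200 range needs FINAL MAX ≤ INITIAL MAX. A FINAL MAX of 42 against 40 gives 205 as written and −5 with the minus. That should be uncommon, because INITIAL MAX is the best of three attempts.

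**Effect on a between-arm comparison of means.** Since one index is 200 minus the other, the constant cancels: the difference in means changes sign, and the standard deviation is unchanged. One simulated data set illustrates this, with 120 per arm, INITIAL MAX drawn with mean 40 and SD 8, and retained fraction drawn with mean 0.75 in one arm and 0.70 in the other, SD 0.10 (all assumed except the 120 per arm):

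- As written: difference +2.52, t = 2.185, p = 0.030.
- With minus: difference −2.52, t = −2.185, p = 0.030.

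**Effect on a relative comparison.** Suppose the minus-sign decrement falls from 25 to 20. That is (25 − 20)/25 = a 20% reduction. As written, the same data go from 200 − 25 = 175 to 200 − 20 = 180, which is 5/175 = a 2.9% increase. Here both direction and size are wrong.

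**The case against.** The strongest reply concerns weight, and most of it stands. Appendix E presents this index as one of some additional calculated quantities. It appears in no objective (Section 6), no research question (Section 8), no primary or secondary endpoint, no sample-size input and no analysis named in Section 15. INITIAL MAX, FINAL MAX, duration and work are all kept alongside it, so a conflict would be visible and the index can be rebuilt without loss of data.

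Three stronger readings are tempting, and the documents support none of them.

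- *A reader might infer that the trial's finding on carnosine would be reversed.* No listed endpoint uses this index. Reporting benefit as harm would also require literal coding, nobody questioning decrements between 100 and 200, and interpretation without the raw grip values.
- *A reader might infer that test results on the index would be invalid.* In a t-test or linear mixed model, only the sign changes.
- *A reader might infer that the written value is meaningless.* Subtracting 100 gives percent strength retained. The value is mislabelled and offset, but it can still be read.

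Two cautions about the evidence also stand. A minus sign can be altered when text is extracted from PDF. The neighbouring operators in the sentence are not minus signs, so their correct rendering does not settle the matter; hyphens do survive elsewhere, as in the freezer temperatures. Moreover, Appendix E refers to a cited source for the test method. That source is not available here, so the minus form cannot be checked against it.

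None of this removes the contradiction between name and formula on the face of the plan.

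**Conclusion.** The point holds as a minor correction to a derived-variable definition. As printed, the index equals 100(1 + r), runs from 200 with no loss down to 100 with total loss, and so contradicts its own name. A between-arm difference in means keeps its absolute size and p-value and reverses its sign. Percent changes and ratios are distorted in both direction and size.

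The conclusion rests on three assumptions: that the plus sign is on the source page; that the index is meant to measure loss, as its name says; and, for the 100 to 200 range only, that FINAL MAX does not exceed INITIAL MAX. The trial's primary and secondary conclusions are not affected.

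**What to change.** First confirm the sign on the source page and in the method that Appendix E cites. If the plus sign is there and the cited method does not define the index differently, replace the formula in Appendix E with:

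SDI = 100 × (INITIAL MAX − FINAL MAX) / INITIAL MAX

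Add one sentence saying that 0 means no loss of strength, that higher values mean more fatigue, and that a negative value is possible if FINAL MAX exceeds INITIAL MAX. Use the same definition in any derivation program.

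The cost is one character and one sentence. No measurement, visit or participant procedure changes, and any values already derived can be recomputed from the recorded grip readings, or converted as 200 minus the written value. It is best done before the physical function data are analysed, so that it does not look like a change made after seeing results.
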